7. PROTOCOL DEVIATIONS/VIOLATIONS

The protocol deviations/violations will be identified and assessed by clinical research physician or designee following company standard operational procedure. These protocol deviations/violations will be summarized by treatment group for the ITT population.

Protocol deviations and violations will be reviewed prior to database hard lock. Major protocol violations will be used to determine the mITT population (defined in Section 5.2.2).

Major protocol deviations and violations will be summarized using frequency tabulations. A by-subject listing of subjects with all protocol deviations/violations in the ITT population will be provided.

8. DEMOGRAPHICS AND BASELINE CHARACTERISTICS

Demographic and baseline disease characteristics will be summarized by treatment group and overall for the ITT, mITT and safety populations, and for Bridge to HSCT subjects in safety population.

Individual subject listings will be provided to support the summary tables.

8.1. Demographics

Age (year), height (cm), weight (kg), body mass index (kg/m²), body surface area (m²), and other continuous baseline characteristics will be summarized using descriptive statistics (N, mean, standard deviation, median, minimum, maximum), while age group ≥ 60 years and < 70 years, ≥ 70 years and < 80 years, ≥ 80 years), gender, ethnicity, race, geographic region and other categorical variables will be provided using frequency tabulations (count, percent) by treatment group and overall.

Age or year of birth will be recorded on CRF. Where age is not recorded, age will be calculated as follows: Age = year of informed consent – year of birth.

Body mass index (BMI) will be calculated as follows: BMI (kg/m²) = weight in kg / (height in m)².

If not collected in CRF, body surface area (BSA) will be calculated per the Dubois & Dubois formula: BSA (m²) = weight (kg)^{0.425} x height (cm)^{0.725}/139.2.

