### 4.2. Inclusion Criteria

Subjects must satisfy the following criteria to be enrolled in the study:

1. Subject is  $\geq 60$  years of age at the time of signing the ICF
2. Subject has primary (ie, de novo) or secondary (progression of MDS or myeloproliferative neoplasms ([MPN], or therapy-related) AML according to WHO classification ([Appendix B](#))
3. Subject has received second- or third-line of AML therapy (see [Appendix G](#) for the definition of prior AML line; note that, for subjects having AML secondary to prior higher risk [Intermediate-2 or High risk according to the International Prognostic Scoring System] MDS treated with a hypomethylating agent [eg, azacitidine or decitabine], the hypomethylating therapy can be counted as a line if there is disease progression to AML during or shortly [eg, within 60 days] after the hypomethylating therapy.)
4. Subject has the following disease status:
  - a. Refractory to or relapsed after second- or third-line of intensive therapy for AML (eg, the “7 + 3” regimen):  
at least 5% leukemic blasts in bone marrow (the minimum number of treatment cycles of the intensive therapy is per the investigator’s discretion); or
  - b. Refractory to or relapsed after second- or third-line low-intensity AML therapy (eg, LDAC, azacitidine or decitabine):  
at least 5% leukemic blasts in bone marrow after at least 2 treatment cycles
5. Subject is eligible for and willing to receive the pre-selected CCR treatment option, according to the investigator’s assessment (Note: Subjects with degenerative and toxic encephalopathies, especially after the use of methotrexate or treatment with ionizing radiation, should not receive cytarabine.)
6. Subject has Eastern Cooperative Oncology Group (ECOG) performance status of 0, 1 or 2 ([Appendix D](#))
7. Subject has IDH2 gene mutations tested centrally (using the “investigational use only” PCR assay, Abbott RealTime IDH2) in samples of bone marrow aspirate **and** peripheral blood, and confirmed positive in bone marrow aspirate **and/or** peripheral blood. (Note: in the event that the central laboratory result is delayed and precludes acute clinical management of a subject who has confirmed IDH2 gene mutation by local evaluation, the subject may be eligible for randomization with approval by the Medical Monitor.)

8. Subject has adequate organ function defined as:

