10.4. Subgroup Analysis

Appropriate subgroup analyses for primary and key secondary efficacy endpoints (ORR and EFS) by the following subgroups:

1. Age groups (≥ 60 years and < 70 years, ≥ 70 years and < 80 years, ≥ 80 years);
2. Gender (male and Female);
3. Region (North America, South America, Europe, Asia, Australia; US, non-US);
4. Race;
5. Prior systemic anti-cancer therapies for AML (2nd versus 3rd lines);
6. Baseline cytogenetic risk status (better-risk, intermediate-risk, poor-risk, failure);
7. IDH2 gene mutate type (R140 vs. R172);
8. AML initial diagnosis (primary or secondary);
9. WHO classification of AML;
10. ECOG performance status at baseline (Grade 0, 1, 2, 3);
11. Prior intensive therapy for AML (yes versus no) (IVRS and CRF source);
12. Primary refractory (yes versus no) (IVRS and CRF source);
13. Prior allogeneic HSCT for AML (yes versus no) (IVRS and CRF source);
14. ELN risk classification

15. Non-Protocol Definition Primary Refractory, defined as having at least 2 lines prior AML or Higher MDS treatment and never attained CR, Cri, or CRP (yes versus no).

A forest plot will be provided based on the HRs for each subgroup.

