15.1.1. Calculation Using Dates

Calculations using dates (e.g., subject's age or relative day after the first dose of study drug) will adhere to the following conventions:

- Study days after the start day of study drug will be calculated as the difference between the date of interest and the first date of dosing of study drug (e.g., lenalidomide) plus 1 day. The generalized calculation algorithm for relative day is the following:

- If $TARGET\ DATE \geq DSTART$ then $STUDY\ DAY = (TARGET\ DATE - DSTART) + 1$;
- Else use $STUDY\ DAY = TARGET\ DATE - DSTART$.

Note that Study Day 1 is the first day of treatment of study drug. Negative study days are reflective of observations obtained during the baseline/screening period. Note: Partial dates for the first study drug are not imputed in general. All effort should be made to avoid incomplete study drug start dates. Some analyses may exclude subjects without study drug start date. The SAP may be amended on a case-by-case basis, including guideline and suggestion such as imputing Day 1 by consent date of treated subject.

- Age (expressed in days) is calculated: $AGE = CONSENT - DATE\ of\ BIRTH + 1$. In practice, age will be transformed to years by dividing the difference by 365.25 days, then truncating.
 - Preference is for using calculated age from clinical database. When not available, calculated age from CRF or IVRS may be used
 - Partial birth date: impute missing day as 15th of the month; impute missing month as July; set missing age for missing year
- Intervals that are presented in weeks will be transformed from days to weeks by using (without truncation) the following conversion formula:

$$WEEKS = DAYS / 7$$

- Intervals that are presented in months will be transformed from days to months by using (without truncation) the following conversion formula:

$$MONTHS = DAYS / 30.4375$$

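### SAP 8.1 and SAP 15.1.1 give conflicting age rules for subjects with only a birth year, and the 8.1 rule errs only upward

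*SAP*

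**What the plan says.** SAP 8.1 (Demographics) describes what is collected: "Age or year of birth will be recorded on CRF". It then gives the fallback: "Where age is not recorded, age will be calculated as follows: Age = year of informed consent – year of birth". Recorded age therefore comes first, and calculation is used only when it is missing.

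SAP 15.1.1 (Calculation Using Dates) takes age in days as consent date minus birth date plus one. It continues: "In practice, age will be transformed to years by dividing the difference by 365.25 days, then truncating". For incomplete birth dates: "Partial birth date: impute missing day as 15th of the month; impute missing month as July; set missing age for missing year". A birth date known only to the year thus becomes 15 July of that year. On the order of sources it says: "Preference is for using calculated age from clinical database", with age from the CRF or IVRS as the fallback.

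Age groups are used in the demographic tables (SAP 8.1), in the subgroup analyses of OS, ORR and EFS (SAP 10.4: "Age groups (≥ 60 years and < 70 years, ≥ 70 years and < 80 years, ≥ 80 years") and in the TEAE subgroups (SAP 11.1).

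**The concern.** A difference of calendar years is completed age only for someone whose birthday falls on or before the consent date. For everyone else it is one year too high, and it can never be too low, so the errors do not cancel.

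The SAP also gives two rules for the same subject, and opposite preferences between recorded and calculated age, without saying which section governs. SAP 13, which lists changes from the protocol's analyses, does not mention it. Two programmers could each follow the SAP and produce different age variables.

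At stake are the mean and median age by arm and the membership of the age groups cut at 70 and 80.

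**Working it through.** The documents give no error rate for either rule, so there is no stated figure to reproduce. The check compares each rule with true completed age.

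**Inputs.** The two rules come from SAP 8.1 and 15.1.1, the cut points 70 and 80 from SAP 10.4, and the planned 316 subjects from SAP 4.1. Assumptions: birth dates and consent dates are uniform over the year and independent. The share of subjects with only a birth year is not given, so a range is shown.

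**Illustration.** Take a birth year of 1948 and consent on 1 March 2018.
- SAP 8.1: 2018 − 1948 = 70.
- SAP 15.1.1: 15 July 1948 to 1 March 2018 is 25,431 days; (25,431 + 1)/365.25 = 69.6, truncated to 69.
- If the subject was born in October 1948, the true age is 69, and SAP 8.1 puts the subject in the 70 to <80 group.

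**Error of each rule.** Let p be the fraction of the year before 15 July, 195/365 = 0.534.
- SAP 8.1 is one year high when the birthday falls after consent: probability about 1/2. It is never low. Mean bias is about +0.5 year.
- SAP 15.1.1 is one year low when consent is before 15 July and the birthday has already passed: p²/2 = 0.534²/2 = 0.143.
- SAP 15.1.1 is one year high when consent is on or after 15 July and the birthday is still to come: (1 − p)²/2 = 0.466²/2 = 0.109.
- SAP 15.1.1 is therefore right in about 1 − 0.143 − 0.109 = 0.75. Mean bias is 0.109 − 0.143 = −0.03 year.
- The rules disagree whenever consent falls before mid-July: about 53%.

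Enumerating 365 × 365 day pairs for four pairs of years agrees: SAP 8.1 high in 49.6–49.9% and low in none; SAP 15.1.1 low in 14.2–14.5% and high in 10.7–10.9%; disagreement 53.2–53.4%.

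**Movement across 70 or 80.** Under SAP 8.1 only subjects in the year below a cut point can move, and about half of them do. With ages uniform over 60–90 this is 2 × (1/30) × 0.5 = 3.3%. Simulation over an assumed 42-month enrolment window gave:

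| Assumed age distribution | SAP 8.1, moved up | SAP 15.1.1, wrong group (either direction) |
|---|---|---|
| Uniform 60–90 | 3.3% | 1.6% |
| Uniform 60–85 | 4.0% | 1.9% |
| Normal, mean 71, SD 6, truncated at 60 | 4.6% | 2.1% |

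The last column counts any derived age under 70 as the lowest group, so an eligible subject whose derived age is 59 is not counted as misplaced.

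**Scale under SAP 8.1.** Subjects one year high = 0.5 × n; subjects regrouped = 0.033 × n to 0.046 × n.

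| Year-only share of 316 | n | One year high | Change age group |
|---|---|---|---|
| 0% | 0 | 0 | 0 |
| 10% | 31.6 | about 16 | 1.0–1.5 |
| 25% | 79 | about 40 | 2.6–3.6 |
| 50% | 158 | 79 | 5.2–7.3 |
| 100% | 316 | 158 | 10.4–14.5 |

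**The case against.** The strongest reply is that the 8.1 formula may never be used. It applies only where age is missing, and Protocol 6.1 lists age among the demographics collected at screening. No document shows that any subject lacks it. This stands: the affected number is unknown and may be zero. The conflict over whether recorded or calculated age comes first would remain even then.

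The consequence is also small. Age is not a stratification factor (SAP 4.3) and does not enter the primary OS analysis (SAP 10.2). The age subgroups lie outside the testing sequence (SAP 10.1), and the same rule applies in both arms. All of this stands.

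SAP 15.1.1 is not exact either. It makes about 14% of year-only subjects a year too young, so a true 60-year-old can be derived as 59 and fit none of the age groups. Merely pointing to that section would also import its preference for calculated age. Both points stand and shape the fix.

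A reader might go further and infer that the upward error weakens the lower age limit, by showing a 59-year-old as 60 and so keeping an ineligible subject in the mITT population. The documents do not support that. Protocol 4.2 sets the limit on "years of age at the time of signing the ICF", as an enrolment criterion. Deviations are found by review: "The protocol deviations/violations will be identified and assessed by clinical research physician or designee following company standard operational procedure" (SAP 7). Nothing says that this review, or the mITT exclusion in SAP 5.2.2, uses the age derived under SAP 8.1.

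**Conclusion.** The point holds, as a minor one. For a subject with only a birth year, SAP 8.1 gives either the correct age or one year too many. SAP 15.1.1 gives a different rule and the opposite source order, with no precedence stated.

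Under uniform birthdays and consent dates, SAP 8.1 is one year high for about half of year-only subjects and the two rules disagree for about 53%. About 3.3–4.6% of year-only subjects would move up an age group, depending on the assumed age distribution, against about 1.6–2.1% misplaced in either direction under SAP 15.1.1. In subjects, this ranges from none, if every age is recorded, to about 10–15 regrouped if none is.

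The effect reaches age summaries and descriptive age subgroups only. The primary OS test is untouched, and no bias in the eligibility check or in mITT membership follows from the documents.

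**What to change.** Delete the year-difference formula from SAP 8.1, and state one rule and one source order in both 8.1 and 15.1.1: recorded age at consent if present; otherwise the 15.1.1 derivation with 15 July imputed for a missing day and month. Use that one age variable for the summaries and all age subgroups.

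Add a sentence saying that a derived age of 59 caused only by the imputation is placed in the 60 to <70 group and is not by itself treated as an eligibility violation.

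The cost is a few sentences and one derivation, with no new data. The remaining drawback is that year-only ages stay approximate: about 11% one year high and 14% one year low. The mean bias, however, falls from about +0.5 to about −0.03 year.

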8.2. Baseline Disease Characteristics and AML Diagnosis History

The number and percentage of subjects in each of the following categories will be summarized by treatment group and overall. Continuous variable will be summarized by mean, standard deviation, median, minimum, and maximum.

Depending on the way in which data is collected, information on the same CRF page will be listed in one listing. Multiple listings will be provided for the information above.

8.2.1. Baseline Disease Characteristics

1. IDH2 gene mutate type (R140 or R172);
2. Eastern Cooperative Oncology Group (ECOG) performance status;
3. Prior intensive therapy for AML (yes versus no);
4. Prior refractory (yes versus no);
5. Prior stem cell transplants for AML (yes versus no; if yes, type);
6. Prior systemic anti-cancer therapies for AML;
7. Time (days) from last prior HSCT, calculated from starting date of the last prior HSCT to randomization date (≤ 100 days; > 100 days to ≤ 365 days; > 365 days);

8. Bone marrow blasts (%) and category (< 20%; 20% to < 30%; 30% to < 50%; ≥50%) from the screening bone marrow aspirate sample (local, central) and bone marrow biopsy sample (local, central);
9. Peripheral blood blast (%) (local, central);
10. Cytogenetic Risk Status (better-risk, intermediate-risk, poor-risk, failure, normal, not done) (local);
11. Select Chromosomal Abnormalities at Baseline;
12. Co-occurring mutations (FLT3-ITD, NPM, TET2, IDH1) if data is available;
13. Baseline values of the following lab parameters: Hemoglobin (< 80 g/L, ≥ 80 g/L), platelet count (< 50 x10⁹/L, ≥ 50 x10⁹/L), absolute neutrophil count (ANC) (< 0.5 x10⁹/L, 0.5 to < 1 x10⁹/L, ≥ 1.0 x10⁹/L), white blood cells (WBC) (<15 x10⁹/L, 15 to < 30 x10⁹/L, ≥ 30 x10⁹/L), creatinine clearance (< 45 mL/min, 45 to < 60 mL/min, ≥ 60 mL/min);
14. Number of transfusions and number of units transfused of red blood cell (RBC) and platelets within 56 days prior to randomization, and baseline transfusion dependence for both RBC and platelets.
15. Left Ventricular Ejection Fraction (LVEF) from Echocardiogram and Multigated Acquisition (MUGA)
16. Prior lines of AML Treatment and category (0 lines, 1lines, 2 lines, 3 lines, 4 lines, >4 lines), Prior refractory status, and prior relapse status
17. Best response to Prior lines of AML Treatment, split by Low-Intensity AML Therapy and Intensive Chemotherapy for First line, Second Line, Third Lines, Fourth Line, and Last line of prior AML treatment

8.2.2. AML Diagnosis History

1. WHO Classification
2. AML initial diagnosis: primary (i.e., de novo) or secondary (MDS progression or myeloproliferative neoplasms (MPN), or therapy-related) according to WHO classification. If AML is secondary, number and percentage of subjects who has an antecedent hematologic disorder will be summarized, and type of disorder will be tabulated too;
3. IPSS Classification for subjects with Higher Risk MDS
4. Time (month) from the initial diagnosis of AML, calculated from time of initial diagnosis to randomization date.

8.3. Medical History and Concomitant Disease

The medical and surgical history, as well as concomitant disease will be summarized by the Medical Dictionary for Regulatory Activities (MedDRA) latest version by system organ class (SOC) and preferred term (PT) for the ITT population and safety population. Active concomitant disease will be summarized in separate tables.

8.4. Prior/Concomitant/Follow-up Medications/Procedures/Therapies

Prior medications/procedures/transfusions are defined as medications/procedures/transfusions that were started prior to start of study treatment (start of study treatment refers to randomization date for BSC only group and first dose of study drug for other treatment groups) or have start dates missing. If start date is missing and end date is before start of study treatment medication will be classed as prior only.

Concomitant medications/procedures/transfusions are defined as non-study medications/procedures/transfusions that are started on or after the start of study treatment but before the end of the study treatment period or started before the start of the study treatment and ended or remain ongoing during the study treatment. For non-BSC groups, the end of the study treatment period is defined as the earlier date of last dose of study drug + 28 days and date of death. For BSC groups, the end of the study treatment period is defined as the earlier date of discontinuation from the treatment period and date of death.

Medication/procedure/transfusion with missing start date but end date on or after start of the study treatment (randomization date for BSC only group) and before the end of the study treatment period or with both missing start date and end date is also considered as concomitant medication/procedure/transfusion.

Follow-up medications/transfusions are defined as non-study medications/transfusions that are started after the date of the end of the study treatment period. All non-study medications and therapies will be coded by Anatomical Therapeutic Chemical (ATC) code and PT using the World Health Organization Drug Dictionary latest version. All procedures and surgeries will be coded by the Medical Dictionary for Regulatory Activities (MedDRA) latest version by system organ class (SOC) and preferred term (PT).

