## 1. JUSTIFICATION FOR AMENDMENT

[figure not shown]
Significant changes included in this amendment are summarized below:

- ***Sample size was increased and statistical considerations were updated.***

AG-221 (enasidenib) was approved by the Food and Drug Administration (FDA) in the United States (US) for the treatment of adult patients with relapsed or refractory AML with an isocitrate dehydrogenase 2 (IDH2) mutation as detected by an FDA-approved test. This approval may allow subjects in the conventional care regimen arm to receive commercially available AG-221 (enasidenib), leading to statistical power loss in detecting the treatment effect on overall survival. To remedy this statistical power loss, Study AG-221-AML-004 increased sample size from 280 to 316 subjects and updated statistical considerations (eg, event size was increased from 193 to 250 deaths, etc). (Refer to the Protocol Summary, Section 3.1.1, Figure 1, Section 4.1, and Sections 9.3, 9.6.1, and 9.8.)

- ***Study duration was updated.***

The expected duration of this study was changed from approximately 28 months to 78 months because the enrollment period was extended from 24 months to 42 months to increase the sample size as mentioned above, and to submit the final study report and data set with 3 years of follow-up per the Post Marketing Requirements by the FDA (NDA 209606 APPROVAL 1-Aug-2017 Reference ID: 4132874). Accordingly, the definition of the End of Trial has been updated as either the date of 36 months from the last subject randomized date, or the date when all subjects discontinued from study treatment and no subject is available for survival follow-up, whichever is the later date. (Refer to the Protocol Summary, Table 2, Sections 3.2 and 3.3.)

- ***Fasting (preferred) lipid panel was added at 2 more timepoints.***

Fasting (preferred) lipid panel was added on Day 1 of Cycles 2 and 3 to allow for monitoring lipid changes during early cycles of study treatment. (Refer to Table 3.)

- ***The fasting requirement for lipid panel was updated.***

The most recent European guideline indicates that non-fasting blood samples are sufficient for assessing plasma lipid profiles (Nordestgaard, 2016). Thus, the fasting requirement for lipid panel was updated, particularly for subjects who experience clinically meaningful elevations of lipids, per the investigator's assessment. (Refer to Table 3 and Section 6.2.)

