8.4.3. Prior/Follow-up Anti-Cancer Therapies

This section includes both AML therapies and non- AML therapies. AML therapies include surgery, radiation, systemic or any other therapy for the subject's AML disease, particularly intensive AML chemotherapies as induction/re-induction/salvage chemotherapies, consolidation or maintenance therapies, HSCT, low-intensity AML therapies such as azacitidine, decitabine or LDAC, or other medications considered supportive care for AML, regardless of discontinuation

date of treatment. Non-AML therapies may consist of the same therapies like AML therapies but for other hematologic or non-hematologic malignancies.

All tables described in this section will be produced on both ITT and safety population.

Prior and follow-up therapies will be summarized separately in tables.

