8.4.3.3. Systemic Anti-Cancer Medication for AML

The number and percentage of subjects with any prior/follow-up systemic anti-cancer medication for AML will be presented by treatment group and overall for ITT and safety populations. A similar summary will also be presented for medication for AML or Higher Risk MDS. A summary of the Follow-up AML therapies, and their associated responses will also be presented. For subjects with systemic anti-cancer therapy for AML, detailed information will be presented in a listing.

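### The 28-day rule in SAP 8.4 keeps AML drugs started soon after the last dose out of the follow-up AML therapy tables, to an extent that differs by regimen

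*SAP*

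**What the plan says.** SAP 8.4 sorts non-study medications by start date. Concomitant ones include those "that are started on or after the start of study treatment but before the end of the study treatment period". For follow-up, "Follow-up medications/transfusions are defined as non-study medications/transfusions that are started after the date of the end of the study treatment period".

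The end of that period depends on the regimen. For the four drug regimens it is "the earlier date of last dose of study drug + 28 days and date of death". The rule for BSC-only differs: "the end of the study treatment period is defined as the earlier date of discontinuation from the treatment period and date of death".

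SAP 8.4.3, on anti-cancer therapies, gives no definition of follow-up of its own and says: "Prior and follow-up therapies will be summarized separately in tables". SAP 8.4.3.3 presents systemic AML medication as prior or follow-up, for the ITT and safety populations, and adds: "A summary of the Follow-up AML therapies, and their associated responses will also be presented". By contrast, SAP 8.4.3.1 names prior, concomitant and follow-up for anti-cancer procedures.

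Protocol 6.3 collects subsequent AML therapies and the response to them once study treatment has stopped, and states no lag. Protocol 8.2 says that a subject who needs another AML therapy should come off study treatment.

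**The concern.** Under the protocol, a new AML drug begun shortly after the last dose is a post-discontinuation therapy. Under SAP 8.4 the same drug is concomitant if it starts inside the 28-day window. Because 8.4.3.3 has no concomitant category, the drug drops out of the tables meant to show what subjects received next and how they responded.

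Those tables matter here. The protocol's amendment justification explains the increase from 280 to 316 subjects and from 193 to 250 deaths by noting: "This approval may allow subjects in the conventional care regimen arm to receive commercially available AG-221 (enasidenib), leading to statistical power loss". The same amendment added collection of response to subsequent AML therapy. A reader weighing the OS result will look to the follow-up therapy table for the extent of switching. If the table undercounts, and does so by different amounts in the two arms, it misdescribes the comparison it is meant to explain.

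**Working it through.** There is no stated figure to reproduce; the point is a classification rule. The check is date arithmetic, followed by a sensitivity calculation.

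**Lag from last dose.** From SAP 8.4: 28 days for AG-221, azacitidine, LDAC and IDAC; 0 days from discontinuation for BSC-only. A drug started exactly on the end date is neither before the end nor after it, so it falls in neither class.

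**Example.** A subject stops LDAC and starts commercial AG-221 12 days after the last dose. Since 12 < 28, the drug is concomitant and absent from the 8.4.3.3 tables. A BSC-only subject who starts the same drug 12 days after discontinuation is counted.

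**After a completed last cycle.** Suppose dosing runs on consecutive days from Day 1, so the last dose falls on cycle day d (Protocol 7.2), and the subject leaves treatment at cycle Day 28. The SAP period ends on day d + 28, so the days past Day 28 still excluded are g = (d + 28) − 28 = d.

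| Regimen | d | End of period (cycle day) | g |
|---|---|---|---|
| AG-221 | 28 | 56 | 28 |
| LDAC | 10 | 38 | 10 |
| Azacitidine | 7 | 35 | 7 |
| IDAC | 3 to 6 | 31 to 34 | 3 to 6 |
| BSC-only | – | discontinuation | 0 |

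**Share left out.** The documents do not give the time from stopping to the next therapy. Assume an exponential gap from Day 28 with median m days. The share left out is 1 − exp(−ln 2 × g/m).

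| m (days) | AG-221 | LDAC | Azacitidine | IDAC | BSC-only |
|---|---|---|---|---|---|
| 14 | 75% | 39% | 29% | 14–26% | 0% |
| 21 | 60% | 28% | 21% | 9–18% | 0% |
| 28 | 50% | 22% | 16% | 7–14% | 0% |
| 60 | 28% | 11% | 8% | 3–7% | 0% |

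For instance, AG-221 at m = 14 gives 1 − exp(−ln 2 × 28/14) = 1 − 0.25 = 75%.

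The model lets no switch happen before cycle Day 28. The LDAC example is a mid-cycle switch and lies outside it. A subject who stops mid-cycle still has the full 28 days from last dose, so early stopping raises the CCR shares.

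**The case against.** The strongest reply is that the exclusion depends on carrying the 8.4 definition into 8.4.3. The defining sentence names only medications and transfusions, so it does not govern transplants (8.4.3.5). The follow-up AML therapies in 8.4.3.3 could also mean the protocol's Follow-up Phase data, which carry no lag. SAP 10.3.2.9 uses a no-lag meaning when it counts HSCT directly after study drug. For transplants this stands: follow-up HSCT is undefined rather than shown to be omitted. For AML medication it does not remove the problem, because 8.4 is the only definition the SAP supplies and its heading covers therapies.

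Second, the records are not lost. They appear among concomitant medications (SAP 8.4.1) and in the listing under 8.4.3.3, and the disposition table has a category for moving to commercial treatment. That stands, but the 8.4.1 table covers the safety population only and carries no response.

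Third, a reader might infer that most prompt switches to commercial AG-221 are missed. The documents do not support this. Such switching is a CCR-arm matter, and in the table above the CCR shares are 0–39% for medians of 14 days or longer. Shares of half or more arise only in the AG-221 arm and only under short assumed gaps.

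Fourth, a reader might infer that the OS and EFS sensitivity analyses inherit the omission. SAP 10.2 and 10.3.1.2 refer to subsequent or new therapy and to off-protocol AG-221, never to the follow-up class of 8.4. No such link is stated.

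**Conclusion.** The concern holds as a fault in the descriptive reporting of subsequent therapy. Read as written, SAP 8.4 and 8.4.3.3 omit AML drugs started within 28 days of the last dose of AG-221, azacitidine, LDAC or IDAC, and omit none started after discontinuation of BSC-only. The rule and its inequality by regimen follow from the text. After completed cycles, the understatement is greatest in the AG-221 arm.

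Its size rests on assumed gaps: 75–50% for AG-221 at medians of 14 to 28 days and 28% at 60 days, with smaller shares for the CCR regimens. The documents cannot say which median applies. The primary OS test is unaffected, and the OS and EFS sensitivity rules are not tied to this class, although the SAP leaves their subsequent-therapy date undefined. The plan should be corrected because these tables are where switching would be read when OS is interpreted.

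**What to change.** In SAP 8.4.3, define follow-up (subsequent) anti-cancer therapy, including HSCT, as any non-study anti-cancer therapy started after the last dose of study drug, or after treatment discontinuation for BSC-only, with no 28-day lag. Exclude hydroxyurea and other permitted best supportive care. The exclusion is needed because 8.4.3 counts supportive medication for AML as AML therapy, and IDAC subjects may continue on BSC after IDAC ends.

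Use this definition in 8.4.3.3 to 8.4.3.5. State that the same start date is the subsequent-therapy date in the OS sensitivity analyses (10.2) and the EFS censoring rules (10.3.1.2), with each item keeping its own scope of therapies. Keep the 28-day rule for ordinary concomitant medications.

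The cost is a few lines of SAP text and one derived flag, best settled before the final database lock. No new data are needed, since subsequent AML therapies are already collected every 4 weeks under Protocol 6.3.
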